## **9.7. Disease-Related Events and/or Disease-Related Outcomes Not Qualifying as AEs or SAEs**

Disease progression does not constitute an AE itself; however, the symptoms/diagnosis leading to disease progression must be reported as AE or SAE accordingly.

## **9.8. Reporting to Competent Authorities and Ethics Committees**

The IB(s) will be the reference document for reference safety information.

The safety vendor is responsible for submission of suspected unexpected serious adverse reactions (see Appendix 3 I for a definition) to health authorities and Institutional Review Boards (IRB)/Independent Ethic Committees (IEC) in accordance with local regulations.

The investigator is responsible for informing the IRB/IEC in a timely manner and in accordance with local procedures.

# **10. STATISTICAL CONSIDERATIONS**

## **10.1. Phase II**

### **10.1.1. Sample Size Determination**

No formal sample size calculation was performed for this trial. The sample size was based on pragmatic considerations in this new and urgent setting with very limited knowledge about the disease.

For the Phase II part of the trial 30 patients were randomized in a 1:1 ratio to treatment Arm A (SBC + IFX-1) and Treatment Arm B (BSC).

### **10.1.2. Analysis Sets**

All analyses were to be performed based on all randomized patients.

### **10.1.3. Statistical Analyses**

The statistical analysis plan (SAP) was developed and finalized as soon as possible after clinical trial application approval. The SAP includes the exact definition of endpoints and variables to be analyzed, extensive details on the statistical analysis methods to be used together with the structure of tables and figures to be included as end-of-text tables and figures as well as appended listings for the clinical study report. It also describes procedures for accounting for missing, unused, and spurious data. This section is a summary of the planned statistical analyses of the primary and secondary endpoints for Phase II of this study.

Individual data were to be listed. Data were to be summarized using suitable descriptive statistics; depending on the structure of the data, summary statistics (e.g., number of observations, mean, standard deviation, minimum, median, maximum, lower quartile, upper quartile) or frequency tables may have been used.

All data were to be displayed by treatment arm if not specified otherwise.

#### **10.1.3.1. Efficacy Analyses**

The relative change (%) from baseline (day 1 prior to study drug administration at  $\pm 1$ h of randomization) in oxygenation index ( $\text{PaO}_2 / \text{FiO}_2$ ) in supine position at day 3, 5, 9, and 15 was to be analyzed with a linear repeated measures model with post-baseline time points as outcome variable and baseline value as explanatory variable. Deceased patients were to be included in the model with an outcome of 0 after death. Patients discharged from the ICU whose oxygenation index was no longer be assessed were to be analyzed by last observation carried forward. Treatment arm, time point, the interaction between treatment arm and time point, the interaction between baseline and time point, age, sex, and intubation status at baseline was to be included as further explanatory variables. The model was to use an unstructured covariance matrix and make use of the Kenward-Roger degrees of freedom approximation. Least square mean differences between treatment arms and their 95% confidence interval was to be calculated and displayed for each time point separately (day 3, 5, 9, and 15), with the evaluation at day 5 reflecting the primary endpoint. If oxygenation index was to be used as the primary endpoint for a Phase III part of the study, data from both study parts were planned to be analyzed in one combined model as specified above with study part as a random effect.

Early response, late response and reaching ICU discharge alive were to be analyzed as three separate time-to-event variables. Withdrawing early from the study would have led to the patient

being right-censored at the date of withdrawal provided that the reason was not an outcome of interest for the time-to-event endpoint. In order to adequately account for competing outcomes as well as potential right-censoring due to varying follow-up times, these outcomes were to be non-parametrically analyzed using Aalen-Johansen-type estimation based on a competing risks model with two absorbing states (event 1: all-cause death; event 2: early response/late response/ICU discharge respectively). The Aalen Johansen estimator estimates the expected relative number of patients (cumulative incidence function [CIF]) of the event at hand. Treatment effects were to be derived in terms of the absolute differences between the treatment arm-specific estimators evaluated at day 7:

$$[\text{Effect}]_{-(Y;7)} = \text{CIF}_Y^A(7) - \text{CIF}_Y^B(7)$$

where  $[\text{CIF}]_{-Y^X}(7)$  is the Aalen-Johansen estimator evaluated at day 7 for endpoint  $Y \in \{\text{Death, Early Response, Late Response}\}$  within treatment group  $X \in \{A, B\}$ . In order to test the hypotheses

$$H_0: [\text{Effect}]_{-(Y;7)} = 0 = 0 \quad \text{vs} \quad H_1: [\text{Effect}]_{-(Y;7)} \neq 0$$

Two-sided confidence intervals (CIs) were to be constructed based on the approximate normality of the estimators ([Beyersmann 2012](#)). Statistical significance was to be concluded if the two-sided 95% CI did not cover 0.

Adjustment for relevant baseline covariates (age, sex, oxygenation index and intubation status) were to be realized by cause-specific Cox models. Subdistribution hazards regression modelling were to be applied in the presence of competing risks ([Fine and Gray 1999](#)) to explore the relative covariate effects in terms of the CIF of interest. Model assumptions were to be checked using graphical diagnostics.

All-cause mortality was to be analyzed as a censored time-to-event variable with Kaplan-Meier methods. The proportion of patients still alive at 28 days was to be derived based on the product limits estimator in each treatment arm. Adjustment for relevant baseline covariates (age, sex, oxygenation index, and intubation status) was to be realized by the Cox proportional hazard model.

The individual components of the composite time-to-event endpoints early and late response and ICU discharge were to be analyzed descriptively.

Laboratory endpoints as well as the Glasgow Outcome Scale were to be analyzed descriptively by time point and treatment arm.

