### 3.2.3. Experience in Humans

At the time of writing of Protocol Version 2.0, Phase II of the current study has been completed and all 30 enrolled patients have been treated (15 in Arm A [best supportive care (BSC) + IFX-1] and 15 in Arm B [BSC alone]) for up to 28 days. Relative change (%) from baseline to day 5 in oxygenation index was assessed as the primary endpoint along with additional clinical parameters until day 28. Relative change in the oxygenation index at day 5 showed no differences between treatment groups. However, IFX-1 treatment was associated with a lower 28-day all-cause mortality when compared to the BSC arm, along with trends in disease improvement, as evidenced by fewer patients experiencing renal impairment assessed by eGFR, more patients showing reversal of blood lymphocytopenia and a greater lowering of lactate dehydrogenase concentrations. In IFX-1-treated patients, pulmonary embolisms (PE) reported as serious adverse events (SAEs) were lower compared to the BSC arm. Also, a temporary increase of D-dimer levels, as potential expression of induction of blood clot lysis, was detected in the first days after initiation of IFX-1 treatment.

Over a treatment period of 28 days, patients in the IFX-1 arm received a maximum of 7 doses of 800 mg IFX-1 intravenously (IV) on separate days. At randomization, 18 patients (60%) were intubated, and 12 patients (40%) had other oxygen supply. A higher number of patients with 2 or more comorbidities associated with increased COVID-19 mortality were reported in the IFX-1 treatment arm compared to the BSC arm. Twenty-eight-day all-cause mortality in the IFX-1 treatment arm was 13% (2 out of 15) versus 27% (4 out of 15) in the BSC arm. In the BSC arm, 4 patients died of COVID-19-induced multi-organ failure, and 3 of them had PE reported as SAEs. In the IFX-1 arm, one patient died after an acute ventilator tube complication (leakage) and one patient with a history of severe chronic obstructive pulmonary disease died of pulmonary failure. Serious AE rates were comparable between groups, but the rate of PE reported as SAEs was substantially lower in the IFX-1 treatment group. Upon review of the safety data, the independent data safety monitoring board has recommended continuation of the trial into Phase III.

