## 4.2. Study Endpoints

### 4.2.1. Phase II

#### 4.2.1.1. Primary Endpoint

The primary endpoint in Phase II was the relative change (%) from baseline (day 1 prior to study drug administration at  $\pm 1$ h of randomization) in oxygenation index ( $\text{PaO}_2 / \text{FiO}_2$ ) in supine position at day 5.

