### **6.1. Phase II**

#### **6.1.1. Inclusion Criteria**

Patients must have met all the following criteria at screening and at enrollment to be randomized into Phase II of the study:

1. At least 18 years of age or older
2. Clinically evident or otherwise confirmed severe pneumonia as evidenced by at least one of the following criteria:
3. Chest X-ray or computed tomography (CT) scan or magnetic resonance imaging (MRI) with pulmonary infiltrates consistent with pneumonia
4. Clinical history in past 14 days of newly developed severe shortness of breath (> 29 breaths / minute) in the absence of oxygen supply or spontaneous peripheral oxygenation  $\leq$  92 with

need for oxygen supply, or need for non-invasive or invasive ventilation (in conjunction with a positive test for SARS-CoV-2 infection)

5. Oxygenation index at time of enrollment ( $\text{PaO}_2 / \text{FiO}_2$ )  $\leq 250$  and  $\geq 100$  in supine position
6. SARS-CoV-2 infection confirmation (tested positive in last 14 days or test results to be obtained within 24h after enrollment, both with locally available test system).
7. No use OR stop of any corticosteroid treatment at time point of enrollment (topical treatment and systemic dose of  $\leq 10\text{mg}$  prednisone / day equivalent allowed)

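### The Phase II primary model scores death as 0, which means unchanged on the relative-change scale; rule and endpoint disagree even if the raw index was meant

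*Combined protocol and SAP*

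**What the plan says.** Section 4.2.1.1 sets the scale: "The primary endpoint in Phase II was the relative change (%) from baseline" in PaO2/FiO2, supine, at day 5. Section 10.1.3.1 takes that relative change at days 3, 5, 9 and 15 as the subject of its opening sentence and says it "was to be analyzed with a linear repeated measures model with post-baseline time points as outcome variable and baseline value as explanatory variable". The next sentence deals with death: "Deceased patients were to be included in the model with an outcome of 0 after death". It gives the 0 no unit. The section then reports least-squares mean differences by day, "with the evaluation at day 5 reflecting the primary endpoint". Protocol Versions 2.0 and 4.0 carry the same rule.

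Section 3.2.3 gives the result: "Relative change in the oxygenation index at day 5 showed no differences between treatment groups". It also reports deaths: "Twenty-eight-day all-cause mortality in the IFX-1 treatment arm was 13% (2 out of 15) versus 27% (4 out of 15) in the BSC arm". Section 10.1.3 describes this text as a summary and refers to a Phase II SAP for exact definitions. That SAP is not among the documents.

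**The concern.** On a relative-change scale, 0 is a neutral score: the patient is as well oxygenated as at baseline. Giving it to patients who have died places death above every fall in PaO2/FiO2. An arm with more deaths is then pulled towards no change, and if survivors are on average getting worse, more deaths improve the arm's mean.

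At stake is how the Phase II primary result is read. Section 3.2.3 reports no difference on this endpoint and then contrasts it with lower mortality on IFX-1. A reader cannot weigh those two statements without knowing how deaths entered the first.

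**Working it through.** **Inputs.** Endpoint scale: 4.2.1.1. Model and value after death: 10.1.3.1. Arm size, 15 and 15, and deaths by day 28, 2 (IFX-1, Arm A) and 4 (BSC, Arm B): 3.2.3. Baseline range: 6.1.1 limits "Oxygenation index at time of enrollment" to 100 to 250. The plan states no figure to reproduce on this point. The two mortality percentages agree with the counts: 2/15 = 13.3% and 4/15 = 26.7%.

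**1. What 0 means on the stated scale.** Relative change = 100 × (post − baseline) / baseline.
- Index of 0 from a baseline of 100: 100 × (0 − 100)/100 = -100. From 250: 100 × (0 − 250)/250 = -100. It is -100% at every baseline.
- A survivor who falls from 150 to 120: 100 × (120 − 150)/150 = -20.
- A patient who has died, under the literal rule: 0. Death ranks above that survivor.

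**2. If the raw index was modelled.** Now 0 is the lowest possible value and the ranking is sensible, but the mean differences are in index units. A fall of 30 units is -30% from a baseline of 100 and -12% from a baseline of 250, so a difference in index units is not a difference in relative change. The day-5 estimate would then not be the endpoint in 4.2.1.1.

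**3. Effect of recoding death from 0 to -100, unadjusted arm means.** Per death: 100/15 = 6.7 points off its arm's mean. Shift in A minus B = 100 × (deaths in B − deaths in A)/15. A positive shift favours IFX-1.

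| Deaths A | Deaths B | Shift in A − B |
|---|---|---|
| 0 | 0 | 0 |
| 1 | 1 | 0 |
| 2 | 2 | 0 |
| 1 | 2 | +6.7 |
| 2 | 4 (28-day split) | +13.3 |
| 0 | 4 | +26.7 |
| 2 | 0 | -13.3 |

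Deaths by day 5 cannot exceed the 28-day counts, so the day-5 shift lies between -13.3 and +26.7.

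**4. The direction can reverse.** This illustration assumes the same survivor mean in both arms and 2 versus 4 dead at the visit.
- Survivor mean -20, death = 0: A = 13 × (-20)/15 = -17.3; B = 11 × (-20)/15 = -14.7; A − B = -2.7, favouring the arm with more deaths.
- Survivor mean -20, death = -100: A = (-260 − 200)/15 = -30.7; B = (-220 − 400)/15 = -41.3; A − B = +10.7.
- Survivor mean +20: A − B is 17.3 − 14.7 = +2.7 with death at 0, and 4.0 − (-12.0) = +16.0 with death at -100.

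**The case against.** The strongest reply is that the raw index was intended. The model sentence speaks of post-baseline time points as the outcome with the baseline value as a covariate, and the last-observation rule for ICU discharge refers to the oxygenation index itself. Both fit a baseline-adjusted model of the raw index, where 0 is the worst score. The Phase II SAP may settle it. This stands as a reason not to assert that deaths were in fact scored as unchanged. It does not repair the text, because the model would then not estimate the stated endpoint and no conversion is described.

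A reader might go further and infer that the rule hid a mortality difference. The documents do not support that. Deaths by day 5 are not reported and may be none. All-cause 28-day mortality is a separate secondary endpoint with its own Kaplan-Meier and adjusted Cox analysis, and 3.2.3 reports it beside the day-5 result. Nor does 3.2.3 say which model or coding lies behind the finding of no difference. It would also be wrong to take the 28-day split as a guide to day 5 and quote a shift of 0 to 13.3 points: early deaths need not follow the 2:4 pattern, so the shift could be larger or of opposite sign.

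The point also has limited reach. Phase II was hypothesis-generating ("No formal sample size calculation was performed for this trial") and is complete. Section 3.2.4 gives variability and dependence on positioning and intubation status as the grounds for dropping this endpoint. The pooled Phase II/III model applied only if the oxygenation index became the Phase III endpoint, which it did not. All of this stands.

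**Conclusion.** The concern holds as a defect in the printed rule. Taken literally, it ranks death above any deterioration; taken as a rule for the raw index, the model no longer yields the relative-change endpoint. Which applied cannot be determined from the documents.

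If 0% was used, the effect on the primary result is unknown within the bounds computed above. The bounds assume 15 patients per arm, day-28 counts as the maximum and -100% as the alternative score. They concern raw means; the planned estimates adjust for baseline, age, sex and intubation status and would move by different amounts. Cumulative deaths cannot fall between visits, so the rule has at least as many deaths to act on at days 9 and 15 as at day 5. Scoring death at -100% is one convention; it matches an index of 0 but is not the only defensible choice.

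No Phase III test, sample size or stopping rule depends on this. The point is worth correcting because 3.2.3 relies on the Phase II result and the check is cheap.

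**What to change.** 1. Establish from the Phase II SAP and the analysis program which outcome scale was modelled and what value was assigned after death. State both in 10.1.3.1 or in the Phase II report, with deaths by arm at days 3, 5, 9 and 15.
2. If 0% was used, re-run the day 3, 5, 9 and 15 model with death scored as -100% (PaO2/FiO2 = 0). Label it post hoc and report it beside the planned analysis. Revise the no-difference sentence in 3.2.3 only if the estimate changes.
3. If the raw index was used, correct the description of the modelled outcome so that it matches what was estimated.

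The recorded rule should not simply be replaced by -100%: the phase was open-label, is complete, and its mortality by arm is known. Any change should be visible and dated.

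Cost: a look at the SAP and program, a paragraph of text and, if needed, one re-run on 30 patients.

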#### 4.2.1.2. Secondary Endpoints

The secondary endpoints in Phase II were:

- Number of patients (%) achieving an **Early Response** as defined as meeting ALL of the following criteria at day 7 after enrollment:
  - Patient alive and extubated OR oxygenation index  $\geq 300$  OR improvement of  $\geq 30\%$  from baseline
  - Temperature  $< 38^\circ\text{C}$  in absence of fever decreasing medication of at least 4h
  - White blood cell count within normal limit of local lab quantifications
- Number of patients (%) reaching a **Late Response** as defined by either being **discharged alive** from hospital until day 28 **OR** meeting ALL of the following criteria at day 28 of the trial
  - Patient alive and extubated
  - Patient discharged from ICU
  - Patient free of shortness of breath (respiratory rate  $< 20$ ) in absence of oxygen supply
  - Patient free of fever ( $< 37.6^\circ\text{C}$ )
- Relative change (%) from baseline (day 1 prior to study drug administration at  $\pm 1$ h of randomization) in oxygenation index ( $\text{PaO}_2 / \text{FiO}_2$ ) in supine position at day 3, 7, 9, and 11.
- All cause 28-day mortality (%)
- Frequency, severity, and relatedness to study drug of treatment-emergent adverse events (TEAEs) and SAEs

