##### **8.1.2.3.2. Evaluation of Late Response**

**Late Response** as defined by either being **discharged alive** from hospital until day 28 **OR** meeting **ALL** of the following criteria at day 28 of the trial:

- Patient alive and extubated
- Patient discharged from ICU
- Patient free of shortness of breath (respiratory rate  $< 20$ ) in absence of oxygen supply
- Patient free of fever ( $< 37.6^{\circ}\text{C}$ )

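### In Phase II the only specified cumulative-incidence test for Late Response is read at day 7, although the endpoint runs to day 28, and the oxygenation model omits secondary days 7 and 11

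*Combined protocol and SAP*

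**What the plan says.** Section 4.2.1.2 gives the Phase II secondary endpoints. Early Response is judged on "criteria at day 7 after enrollment". Late Response has two routes: discharge alive "from hospital until day 28", or "meeting ALL of the following criteria at day 28 of the trial". Section 8.1.2.3.2 repeats the definition. The secondary oxygenation endpoints are relative changes from baseline "in supine position at day 3, 7, 9, and 11", and Section 4.2.1.1 puts the primary oxygenation endpoint at day 5.

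Section 10.1.3.1 then sets out the analysis. Early Response, Late Response and ICU discharge alive are three time-to-event variables with death as the competing event. Treatment effects are the "absolute differences between the treatment arm-specific estimators evaluated at day 7". The quantity in the formula "is the Aalen-Johansen estimator evaluated at day 7 for endpoint" Y, where Y is death, Early Response or Late Response. The decision rule is: "Statistical significance was to be concluded if the two-sided 95% CI did not cover 0". No other time point is given for this contrast.

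The repeated measures model for oxygenation, in the same section and in the synopsis, uses days 3, 5, 9 and 15, with day 5 as the primary evaluation. Protocol version 2.0 carries the same text as version 4.0.

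**The concern.** Day 7 is the time point of Early Response. Applied to Late Response, it gives a test of a different quantity. A confidence interval covering 0 at day 7 would say something about first-week discharge, yet under the stated rule it would be recorded as the result for an endpoint that runs to day 28.

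The oxygenation days raise a smaller problem of the same kind: the endpoint list and the model list do not agree, and two named secondary time points have no contrast in the model.

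What is at stake is how Phase II is reported. The protocol draws on Phase II efficacy data when it chooses the Phase III endpoint (Section 4.2.2.1) and in its benefit/risk statement (Section 3.3), so the secondary results should mean what their labels say.

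**Working it through.** The plan gives no Phase II power or event figure to reproduce. The check compares endpoint days with analysis days, followed by an illustration on assumed rates.

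**1. Response and mortality endpoints**

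| Endpoint | Day in definition | Day of stated analysis | Match |
|---|---|---|---|
| Early Response | 7 | 7 (CIF difference) | yes |
| Late Response | up to 28, or at 28 | 7 (CIF difference) | no |
| All-cause mortality | 28 | 28 (Kaplan-Meier, plus Cox) | yes |
| ICU discharge | time to criteria, no fixed day | in the competing-risks model, not in the set Y | effect formula does not cover it |

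At day 7 nobody can yet have qualified through the day 28 criteria, and discharges on days 8 to 28 have not occurred. The Late Response cumulative incidence at day 7 is therefore the cumulative incidence of live hospital discharge in the first week.

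**2. Oxygenation days**

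- Secondary endpoint days: {3, 7, 9, 11}. Primary: {5}. Model days: {3, 5, 9, 15}.
- Secondary days covered: {3, 9}. Secondary days without a model contrast: {7, 11}. Modelled but neither primary nor secondary: {15}.

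The data were scheduled: Table 1 places disease/response assessments on days 3, 5, 7, 9 and 11, and note b says these include lung function.

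**3. Size, on assumed rates**

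Phase II had 15 patients per arm (Section 3.2.3). The documents give no Late Response or day 7 discharge rates, so the rates below are assumptions. Let a share f of day 28 responses be reached by day 7, equal in both arms, with no early censoring. Then:

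- day 7 difference = f × (day 28 difference)
- P(no event in either arm by day 7) = (1 − f·pA)^15 × (1 − f·pB)^15
- approximate power = Φ[(Δ − 1.96·SE0)/SE1], with SE0 from the pooled rate and SE1 from the two separate rates. At Δ = 0 this gives 2.5%.

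Worked case, 60% against 40% with f = 0.05: the day 7 rates are 3% and 2%, a difference of 1 point. P(no event) = 0.97^15 × 0.98^15 = 0.468.

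| Day 28 rates | Power at day 28 | f | Day 7 difference | Power at day 7 | P(no event) |
|---|---|---|---|---|---|
| 60% v 40% | 18.9% | 0.05 | 1 point | 3.7% | 46.8% |
| | | 0.10 | 2 points | 4.4% | 21.4% |
| | | 0.20 | 4 points | 5.5% | 4.2% |
| 70% v 40% | 37.3% | 0.05 | 1.5 points | 4.4% | 43.3% |
| | | 0.10 | 3 points | 5.4% | 18.3% |
| | | 0.20 | 6 points | 7.5% | 3.0% |
| 60% v 30% | 37.3% | 0.05 | 1.5 points | 4.6% | 50.5% |
| | | 0.10 | 3 points | 5.8% | 25.0% |
| | | 0.20 | 6 points | 8.2% | 5.8% |

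With 0 of 15 in both arms, the estimate is 0 and the normal-approximation variance p(1 − p)/15 is 0 in each arm. The interval collapses to the point 0 and the rule returns not significant. The normal approximation is rough at 15 per arm, so the table shows direction and order of size only.

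**The case against.** The strongest reply is that the section is not the full plan. Section 10.1.3 calls itself a summary and leaves exact endpoint definitions to a Phase II SAP that is not among the documents. That SAP may use day 28 for Late Response and may include days 7 and 11. This stands as a limit on what can be shown. It does not remove the fault in the protocol text, which names day 7 for Late Response and attaches a significance rule.

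Other replies also stand:

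- A reader might infer that 28-day mortality is wrongly read at day 7. It is not. The section gives that endpoint its own Kaplan-Meier estimate at 28 days and an adjusted Cox model.
- A reader might infer that Late Response would come out null whatever happened later. That can be argued only for the day 7 contrast. The cause-specific Cox and Fine-Gray models carry no stated day 7 limit, and the components are described by arm.
- A reader might take first-week discharge to be close to zero. The documents give no such rate, and 12 of 30 patients were not intubated at randomization.
- A reader might infer that days 7 and 11 are never analysed. Section 10.1.3 also plans general descriptive summaries by arm, so only the absence of a stated model contrast can be shown.
- ICU discharge is in the competing-risks model. It lacks only a place in the effect formula, and its definition fixes no day.
- Phase II is complete, was exploratory and unpowered (Section 3.2.4), and had no formal sample size (Section 10.1.1). Results are known, so new contrasts cannot be presented as prespecified.

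**Conclusion.** The point holds in a limited form. As written, the only specified between-arm cumulative-incidence test for Late Response measures first-week live discharge. Two of the four secondary oxygenation days, 7 and 11, have no stated model contrast, while day 15 is modelled without being an endpoint. ICU discharge is left out of the effect formula.

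The documents do not support a broader claim that the Phase II tests miss the secondary endpoints in general. Early Response, 28-day mortality and oxygenation on days 3 and 9 are addressed, as is the day 5 primary endpoint. No Phase III test, alpha or sample size depends on the affected contrasts.

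The mismatch of days follows from the text alone. Its numerical effect rests on assumed rates: over the cases shown, a 20- to 30-point difference at day 28 appears as 1 to 6 points at day 7, and power falls from 19% to 37% at day 28 to about 4% to 8% at day 7. Whether the analysis actually run had this fault depends on the Phase II SAP.

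**What to change.** 1. In Section 10.1.3.1 keep day 7 for Early Response and state the Late Response cumulative-incidence difference at day 28, counting patients who qualify by the day 28 criteria at day 28.
2. Say whether ICU discharge is meant to have an effect measure and, if so, at which day. The documents fix none, so that choice is the sponsor's.
3. Reconcile the oxygenation days with Section 4.2.1.2 by adding contrasts for days 7 and 11 in a supplementary model. Leave the original model and its day 5 primary estimate unchanged. An unstructured covariance has k(k + 1)/2 parameters: 10 for the present four days, and 21 for days 3, 5, 7, 9, 11 and 15. With 30 patients, name a simpler structure as a fallback.
4. Check items 1 to 3 against the Phase II SAP first. If it already uses these days, only the protocol text needs correcting.
5. Label any contrast newly run on the completed Phase II data as post hoc.

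The cost is a text correction and a short supplementary analysis of 30 patients. It needs no new data collection if the assessments scheduled in Table 1 were made.
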